- g. In VOCBP: The serum β-HCG pregnancy test at Visit 0 will be performed using the sample collected for clinical laboratory tests. Before each dosing, urine pregnancy tests will be performed using a commercial kit at the site and the trial subjects will be counseled about the need for consistent and correct use of a highly effective method of contraception.
- h. Leftover blood after completion of the assessments may be used for additional biomarker analyses and/or development of analytical methods.
- i. Trial site personnel will remind the subjects to record the oral body temperature and the worst grade for each symptom in the e-diary at approximately the same time every evening on the day of IMP administration and then every day in the evening for a total of seven consecutive days. Ask/remind the subject to contact the site if they experience any severe or potentially life-threatening reactogenicity events. Trial site personnel will remind the subjects to record the use of antipyretic/analgesic medication to treat symptoms associated with IMP administration for 7 d after each IMP dose using the e-diary.
- j. Only SAEs, adverse event(s) of special interest, AEs that lead to discontinuation or withdrawal, and AEs linked to confirmed COVID-19 cases will be recorded. SAEs must be recorded upon awareness.
- k. For FU visits, only any prohibited medication (including SARS-CoV-2 non-trial vaccinations) will be recorded.
- l. Optimally within 3 d after potential COVID-19 illness onset. All known NAAT-based SARS-CoV-2 positive subjects, from randomization until end of trial, will be asked for an additional unscheduled visit to define the COVID-19 illness as per Section 8.2.8. The COVID-19 illness visit will define the illness as either confirmed COVID-19, unconfirmed COVID-19, or confirmed severe COVID-19.
- m. The results must be available prior to administration of trial treatment at Visit 1.
- n. Blood samples for CCI assessment at "Potential COVID-19 Illness Visit" should only be collected if the visit occurs more than 2 months after the last IMP dose.
- o. This visit will apply to sentinel subjects only.
- p. Visit 6 and Visit 7 can (should ideally) occur on the same day.

- q. Informed consent can be obtained for Dose 2 at either Visit 5, 6 or Visit 7.
- r. Only for subjects that received BNT162b2 Bivalent + BNT162b4 for Dose 1 and who consented to a second (Dose 2).
- s. To be completed before administration of Dose 2.

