5.1 Inclusion criteria

5.1.1 *Inclusion criteria – Cohorts 1 to 4*

Volunteers are eligible to be included in the trial if all of the following criteria apply:

- 1 Have given informed consent by signing and dating the informed consent form (ICF) before initiation of any trial-specific procedures.
- 2 Are willing and able to comply with scheduled visits, treatment schedule, laboratory tests, lifestyle restrictions, e.g., to follow good practices to reduce their chances of being infected or spreading COVID-19, and other requirements of the trial. This includes that they are able to understand and follow trial-related instructions.
- 3 Are aged 18 yrs and older at randomization, have a body mass index over 18.5 kg/m² and under 35 kg/m², and weigh at least 50 kg at Visit 0.
- 4 Are healthy, in the clinical judgment of the investigator based on volunteer-reported medical history data, and physical examination, 12-lead electrocardiogram (ECG), vital signs, and clinical laboratory test outcomes at Visit 0.

Note: Healthy volunteers with pre-existing stable disease (e.g., obesity), defined as disease not requiring significant change in therapy or hospitalization for worsening disease during the 84 d before Visit 0, can be included.

5 Agree not to enroll in another trial with an IMP starting from Visit 0 and until 168 d after receiving the last IMP dose.

Inclusion criteria pertaining to Dose 2: If 168 d after the subject's first IMP dose had passed before they consent to Dose 2, they should agree to not enroll in another trial from the time of consent to Dose 2 until 168 d after receiving Dose 2 of the IMP.

6 Agree not to be vaccinated with:

- Non-trial vaccines (except COVID-19 vaccines, as per next sub-bullet) starting 28 d prior to the Dose 1 and until 28 d after receiving of the last IMP dose. Seasonal influenza vaccine is allowed; however, it should be given at least 14 d before or after any administration of IMP.

Inclusion criteria pertaining to Dose 2: If 28 d after the subject's first IMP dose had passed before they consent to continue Dose 2, they should not have been vaccinated with non-trial vaccines starting from the time of consent to Dose 2 and until 168 d after receiving the Dose 2 of the IMP.

- Non-trial COVID-19 vaccines starting at least 90 d prior to the Visit 1 and until completion of the subject's last trial visit.

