Exclusion pertaining to Dose 2: Subjects who have a change or new onset psychiatric illness.

- 5 Current or history of the following diseases associated with immune dysregulation:
 - Primary immunodeficiencies.
 - History of solid organ or bone marrow transplantation.
 - Asplenia: any condition resulting in the absence of a functional spleen.
 - Currently existing or history of autoimmune disease including and not limited to thyroid autoimmune disease, multiple sclerosis, or psoriasis.

Exclusion pertaining to Dose 2: Subjects who have a change or new onset immunodeficiency.

Prior/concomitant therapy

- 6 Received any non-trial IMP within 28 d before Visit 0 or Visit 7.
- 7 Received or planned treatment throughout the entire trial with radiotherapy or immunosuppressive therapy, including cytotoxic agents or systemic corticosteroids (if systemic corticosteroids are administered for ≥ 14 d at a dose of ≥ 20 mg/d of prednisone or equivalent), e.g., for cancer or an autoimmune disease, or planned receipt throughout this trial. Inhaled/nebulized (except high doses as per [exclusion criteria 3a](#)), intraarticular, intrabursal, or topical (skin or eyes) corticosteroids are permitted.
- 8 Blood/plasma products and/or immunoglobulin containing therapy (including monoclonal antibodies) received within 120 d before Visit 1 or Visit 7 or administration is planned starting at Visit 0 or prior to Visit 7 until 120 d after the last IMP administration in this trial.

Exclusion pertaining to Dose 2: if 28 d after the subject's last IMP dose had passed before they consent to continue Dose 2, blood/plasma products and/or immunoglobulin containing therapy (including monoclonal antibodies) received within 120 d before Dose 2 of IMP (Visit 7) continuously until 120 d after receiving Dose 2 of IMP.

- 9 Received allergy treatment with antigen injections within 28 d before Visit 1 or Visit 7 or where allergy treatment with antigen injections are scheduled within 14 d after any visit with IMP administration in this trial.

- 10 Subjects with a history of SARS-CoV-2 infection (symptomatic or asymptomatic) <60 d prior to randomization.
- 11 Have received any non-RNA or unauthorized COVID-19 vaccine, aside from Dose 1 of the current trial.

Additional exclusions

- 12 Any existing condition which may affect IMP administration and/or assessment of local reactions assessment at the injection site, e.g., tattoos, severe scars, etc.

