6.5 Concomitant therapy

6.5.1 Prohibited concomitant therapies during the trial

(See #6 in the [inclusion criteria for Cohorts 1 to 4](#) and #6 in the [inclusion criteria for Cohort 5](#)) Trial subjects should not have been vaccinated with:

- Non-trial vaccines (except COVID-19 vaccines) starting 28 d prior to Dose 1 and until 28 d after receiving of the last IMP dose (Dose 2). Seasonal influenza vaccine is allowed, however it should be given at least 14 d before or after any administration of IMP.
- Non-trial COVID-19 vaccines until 6 months (168 d) post last IMP dose for Cohorts 1 to 4 and until 28 d post last IMP dose for Cohort 5.
Subjects in Cohorts 1 to 4 that continue to Dose 2 should not have been vaccinated with non-trial COVID-19 vaccines, starting at least 90 d prior to Visit 1 and until completion of the subject's last trial visit.

(See #7 in the [exclusion criteria for Cohorts 1 to 4](#) and #7 in the [exclusion criteria for Cohort 5](#)) Throughout the entire trial, trial subjects should not receive radiotherapy or immunosuppressive therapy, including cytotoxic agents or systemic corticosteroids (if systemic corticosteroids are administered for ≥ 14 d at a dose of ≥ 20 mg/d of prednisone or equivalent), e.g., for cancer or an autoimmune disease, or planned receipt throughout this trial. Inhaled/nebulized (except high doses as per #3a in the [exclusion criteria for Cohorts 1 to 4](#) and #3a in the [exclusion criteria for Cohort 5](#)), intraarticular, intrabursal, or topical (skin or eyes) corticosteroids are permitted.

(See #8 in the [exclusion criteria for Cohorts 1 to 4](#) and #8 in the [exclusion criteria for Cohort 5](#)) Trial subjects should not receive any blood/plasma products and/or immunoglobulin containing therapy (including monoclonal antibodies) from Visit 0 or prior to Dose 2 until 120 d after the last IMP administration for Cohorts 1 to 4, or until 90 d after the last IMP administration for Cohort 5.

(See #9 in the [exclusion criteria for Cohorts 1 to 4](#) and #9 in the [exclusion criteria for Cohort 5](#)) Trial subjects should not receive allergy treatment within 14 d after any visit with IMP administration in this trial.

6.5.2 *Permitted concomitant therapies during the trial*

Seasonal influenza vaccine is allowed; however, it should be given at least 14 d before or after any administration of trial IMP.

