If new symptoms are reported within 4 d after resolution of all previous symptoms, they will be considered to be part of a single illness and a second illness visit is not required;

Surveillance of potential COVID-19 symptoms should continue even if a trial subject has a positive SARS-CoV-2 test earlier in the trial.

During the 7 d following the vaccination, potential COVID-19, symptoms that overlap with specific systemic events similar to COVID-19 infection, should not trigger a “Potential COVID-19 Illness Visit” unless, in the investigator’s opinion, the clinical picture is more indicative of a possible COVID-19 illness than vaccine reactogenicity. If, in the investigator’s opinion, the symptoms are considered more likely to be vaccine reactogenicity, or if the symptoms are equivocal, the investigator may conduct a local SARS-CoV-2 rapid test. If the test result is positive, the symptoms should be recorded as a potential COVID-19 illness; if not, the symptoms that overlap with systemic events should be recorded in the reactogenicity e-diary or as AEs, if not captured in the reactogenicity e-diary.

The trial subject is also instructed to contact the site should they receive a positive SARS-CoV-2 test (NAAT or rapid antigen) to inform the site of the result and the date the test was conducted.

Potential COVID-19 Illness Visit:

This visit should be conducted in person. Telehealth visits are not advised unless the investigator has sufficient justifications with no safety concerns for the trial subject. At minimum, the following details should be recorded by the investigator during “Potential COVID-19 Illness Visits”:

- Any concomitant treatments (if any)
- Confirmation that the trial subject does not require emergent medical care
- Method of COVID-19 diagnosis
- Any AEs, SAEs, AESIs, AEs leading to subject withdrawal/discontinuation
- Outcome of the brief (symptom-directed) physical examination
- Outcome of the rapid antigen test for SARS-CoV-2 infection

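### Cohorts 1 to 4, Dose 2: inclusion criterion 6 and Section 6.5.1 set different windows for non-trial vaccines, and under criterion 6 the look-back before Dose 2 can be 0 d

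*Protocol*

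**What the plan says.** Protocol Section 5.1.1, criterion 6, has three parts that matter here.

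- Its first bullet bars non-trial vaccines other than COVID-19 vaccines from 28 d before Dose 1 until 28 d after the last IMP dose. Seasonal influenza vaccine is allowed with a 14 d gap around any IMP dose.
- Its Dose 2 paragraph applies when 28 d have passed since Dose 1 before the subject consents to Dose 2. It bars "non-trial vaccines starting from the time of consent to Dose 2 and until 168 d after receiving the Dose 2 of the IMP".
- A separate bullet bars non-trial COVID-19 vaccines from 90 d before Visit 1 to the last trial visit.

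Section 6.5.1 cites criterion 6 as its source but states the window for the same vaccines as "starting 28 d prior to Dose 1 and until 28 d after receiving of the last IMP dose (Dose 2", with no break between doses.

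On the timing of consent, a footnote to Table 3 in Section 1.3 says: "Informed consent can be obtained for Dose 2 at either Visit 5, 6 or Visit 7". Another footnote says that Visits 6 and 7 should ideally fall on the same day.

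Other Dose 2 criteria were tied to Visit 7. Exclusion 6 in Section 5.2.1 reads "Received any non-trial IMP within 28 d before Visit 0 or Visit 7", and exclusion 9 does the same for allergy injections.

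**The concern.** The two rules disagree at both ends of the window, and the disagreement at the start has a consequence for the data. Solicited local and systemic events within 7 d of every dose are primary endpoints. A licensed vaccine given a few days before Dose 2 can produce the same fever, fatigue, myalgia or arm pain. After Dose 1 there is at least a randomized arm on BNT162b2 Bivalent against which to read the rates. After Dose 2, which is open-label and given only to prior BNT162b4 recipients, there is none. The 28 d clearance required before Dose 1 is therefore not assured where it would help most.

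The conflict also leaves a deviation undefined. SAP Section 5.2 allows data collected after a key deviation to be excluded, with use of prohibited medication as its example. Whether a vaccine shortly before Dose 2 is a deviation depends on which section is read, and that could decide whether the 28 d post-Dose 2 titer, a secondary endpoint, is kept.

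**Working it through.** The documents give no figure for this point, so the check compares the windows and then shows scale.

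**Does the Dose 2 paragraph always apply?** The earliest consent visit is Visit 5 (Day 90 ± 7, so Day 83 to 97). By then 28 d since Dose 1 have passed, so the condition is always met.

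**Look-back at Dose 2 under criterion 6** (Visit 7 day minus consent day). Visit 6 is Day 180, −10 to +30 d, so Day 170 to 210. Visit 7 is up to 30 d later, so Day 170 to 240.

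| Consent signed at | Look-back before Dose 2 |
|---|---|
| Visit 7 | 0 d |
| Visit 6 | 0 to 30 d |
| Visit 5 | 170 − 97 = 73 d to 240 − 83 = 157 d |
| Dose 1, for comparison | 28 d |

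**Look-back under Section 6.5.1.** The whole interval between doses is barred: 170 − 1 = 169 d to 240 − 1 = 239 d, plus the 28 d before Dose 1.

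**End of the window.** 168 d after Dose 2 (criterion 6) against 28 d (Section 6.5.1): 168 − 28 = 140 d. Criterion 6 is looser at the start and stricter at the end.

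**A case.** Licensed vaccine on Day 170; consent and Dose 2 on Day 180. Under criterion 6 the vaccine came before the bar began and is allowed. Under Section 6.5.1 it is prohibited.

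**Consequence of the end difference.** Events at 7 d and 28 d lie inside both windows. SAEs are followed for 6 months, but every SAE is counted whatever vaccine was received. What changes is recording: at follow-up visits only prohibited medication is recorded (Table 3, footnote k; SAP Table 10 applies it at Visits 10 and 11). A vaccine 60 d after Dose 2 is recordable under criterion 6 and not under Section 6.5.1.

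**Scale in the solicited-event tables.** Planned maximum group sizes are 45 per cohort arm and 90 for 3a with 3b or 4a with 4b.

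- One participant is 1/45 = 2.2 points or 1/90 = 1.1 points.
- For an event otherwise not seen, the Clopper-Pearson 95% upper limit moves from 7.9% (0/45) to 11.8% (1/45), or from 4.0% (0/90) to 6.0% (1/90).
- If a share p of Dose 2 recipients had such a vaccine in the preceding 28 d, the expected number is n × p and the chance of at least one is 1 − (1 − p)^n. The values of p are assumptions:

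| p | n = 45 | n = 90 |
|---|---|---|
| 0.5% | 0.23; 0.20 | 0.45; 0.36 |
| 1% | 0.45; 0.36 | 0.90; 0.60 |
| 2% | 0.90; 0.60 | 1.80; 0.84 |

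These figures show scale only; they are not evidence that it happened.

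**The case against.** The strongest reply is that this is a narrow mismatch of wording. COVID-19 and influenza vaccines have their own rules, which cover Dose 2. The first bullet of criterion 6, read with Dose 2 as the last dose, bars the whole interval, and Section 6.5.1 says so outright. The Dose 2 paragraph could be a transitional rule for subjects enrolled before version 5.0 added Dose 2. The narrow scope stands. The rest does not remove the conflict. Until a subject consents to Dose 2, Dose 1 is the last dose and the first bullet lapses 28 d later; the Dose 2 paragraph then starts afresh at consent. Section 5.1.1.1 requires criteria 1 to 15 for Dose 2, but the paragraph is part of criterion 6.

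It could also be said that exclusion 6 closes the gap, since the Cohort 5 version (Section 13.7.2) makes an exception for influenza vaccine, as if licensed vaccines counted as IMP. The Cohorts 1 to 4 text has no such exception, and Section 6 defines an IMP as a product tested or used as a reference in a trial. A licensed vaccine given in routine care is not that.

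A reader might infer two stronger things.

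- **That the 140 d difference biases the safety results.** It does not reach the 7 d or 28 d endpoints.
- **That SARS-CoV-2 infection around Dose 2 makes the solicited-event tables wrong.** Exclusion 10 is indeed tied to randomization ("Subjects with a history of SARS-CoV-2 infection (symptomatic or asymptomatic) <60 d prior to randomization"), and the testing footnote to Visit 1 ("The results must be available prior to administration of trial treatment at Visit 1"). But the tables count all dosed participants, as the estimand states. Under Section 8.2.8, if reactogenicity seems likelier or the symptoms are equivocal, "the investigator may conduct a local SARS-CoV-2 rapid test"; symptoms with a positive result are recorded as potential COVID-19 illness. Known NAAT-positive subjects "will be asked for an additional unscheduled visit to define the COVID-19 illness", and the SAP lists all NAAT results as well as the solicited events. The NAAT exclusion at the dosing visit in SAP Section 5.1 concerns pre-Dose 1 and immunogenicity. A further table split by swab result would be a preference, not the correction of an error.

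**Conclusion.** The conflict is real and rests on unredacted text. For vaccines other than COVID-19 and seasonal influenza, criterion 6 permits a look-back as short as 0 d before Dose 2, where 28 d applies at Dose 1 and Section 6.5.1 bars the whole interval. The start of the window is the part that matters: it can add events to an uncontrolled 7 d primary endpoint and leaves deviation status open. The end difference affects only what is prohibited, recorded and classed as a deviation in later follow-up.

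The 168 d may be a slip: criterion 5 pairs a 168 d trigger with a 168 d end, criteria 12 to 15 pair 28 d with 28 d, and only criterion 6 mixes them. That is an inference from the pattern.

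Severity is minor. How many participants received such a vaccine is not in the documents; the number is probably small, and any effect would show mainly in uncommon outcomes such as fever or Grade 3 events.

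**What to change.** In the Dose 2 paragraph of inclusion criterion 6, require no non-trial vaccine from 28 d before Visit 7 until 28 d after Dose 2, with seasonal influenza vaccine at least 14 d before or after Dose 2. State the same window in Section 6.5.1. This raises the minimum look-back from 0 d to 28 d, equal to Dose 1, and closes the 140 d gap. It also avoids putting a subject in breach for a vaccine received months before agreeing to Dose 2.

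For participants who have already had Dose 2, record with the SAP Section 5.2 deviation rules which window was used to classify vaccines.

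The cost is one eligibility sentence and its match in Section 6.5.1, with a few Dose 2 administrations delayed. Sample size and the planned safety tables stay as they are.

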5.3 Lifestyle considerations

The trial subjects will be required to remain at the site for \sim 1 hour (h) after each administration of trial treatment. When at the trial site, trial subjects will be asked to drink fluids (e.g., water) per trial site standard for visits with blood draws.

Trial subjects will be asked to avoid strenuous exercise beyond their usual exercise routine for 6 d after each IMP administration after leaving the trial site.

Trial subjects will be required to follow guidance from the trial site personnel on recommended social behaviors to avoid SARS-CoV-2 infection (e.g., mask wearing, social distancing) and to practice the prescribed forms of contraception (see Sections 5.3.1).

Trial subjects will be advised to avoid donating blood or blood products during their participation in this trial.

5.3.1 *Contraception and donation or cryopreservation of germ cells*

Currently, the risk of human teratogenicity/fetotoxicity can NOT be excluded by available data. Therefore, all male and female trial subjects who, in the opinion of the investigator, are biologically capable of having children must agree to use of a highly effective method of contraception consistently (see Section 10.5.2) and correctly (as specified in the SoAs, see Section 1.3 and Section 13.5). In addition, pregnancy testing will be performed at screening and before each IMP administration.

When obtaining informed consent, the investigator or medically qualified designee will inform the trial subject of the need to use highly effective contraception consistently and correctly, and will document the conversation. This will include advice about donation and cryopreservation of germ cells. In addition, the investigator or designee will instruct the trial subject to call immediately if the selected contraception method is discontinued or if pregnancy is known or suspected in the trial subject or partner.

The investigator or his or her designee, in consultation with the trial subject, will confirm that the trial subject has selected an appropriate method of contraception for the individual trial subject and his or her partner(s) from the permitted list of contraception methods and will confirm that the trial subject has been instructed in its consistent and correct use.

VOCBP will only be administered trial treatment after negative pregnancy test outcome(s) at the timepoints indicated in the SoAs (Section 1.3 and Section 13.5).

For definitions of VOCBP, postmenopausal female and fertile men, as well as guidance on how to collect pregnancy information, see Section 10.5.

5.4 Screen failures

Screen failures are defined as individuals who consent to participate in the trial, but did not meet one or more eligibility criteria, and therefore were not eligible for randomization (allocated to IMP).

A minimal set of screen failure information is required to ensure transparent reporting of screening failures to meet the Consolidated Standards of Reporting Trials (CONSORT) publishing requirements and to respond to queries from regulatory authorities. Minimal information includes demography, date the ICF was signed, the reasons for screen failures, and any SAEs, if applicable.

If agreed with the trial Medical Monitor, rescreening is allowed at the discretion of the investigators. Rescreened subjects will need to re-consent and will be assigned a new trial subject number.

